### **Secondary Outcomes of Interest**

Secondary outcomes of interest include the length of hospital stay and Patient-Reported Quality of Life (PRQOL). Both information is already routinely collected through the AHSQC. Length of hospital stay will be recorded in days. PRQOL will be assessed using the HerQLes survey. [20] The HerQLes is a 12-item, validated, a hernia-specific survey that assesses quality of life through abdominal wall function after ventral hernia repair. HeQLes scores will be assessed at baseline and 30 days after the operation. This tool is also part of the patients reported outcomes of the AHSQC.

### **Additional Outcomes of interest**

Pertinent baseline patient demographics, hernia variables, intraoperative details and 30-day outcomes including surgical and medical complications are also captured routinely for all patients in the AHSQC, as a standard of care.

## STUDY PROCEDURES

The interventions are:

- Treatment 1- Administration of a solution of Exparel® combined with Bupivacaine Hydrochloride 0.25% and normal saline, through a bilateral TAP block performed intraoperatively by the attending surgeon, during open ventral hernia repair;
- Treatment 2: Administration of a solution of Bupivacaine Hydrochloride 0.25% and normal saline, through a bilateral TAP block, performed intraoperatively by the attending surgeon, during open ventral hernia repair ;
- Control (Placebo): administration of normal saline through a bilateral TAP block performed intraoperatively by the attending surgeon, during open ventral hernia repair. These formulations were suggested by the fabricant and are already under study in other protocol investigating Exparel at our institution.

INTERVENTION 1 (EXPAREL® + BUPIVACAINE HYDROCHLORIDE 0.25%)	INTERVENTION 2 ( BUPIVACAINE HYDROCHLORIDE 0.25%)	CONTROL GROUP (PLACEBO)

 
• 20cc of Exparel®
 
• 60cc Bupivacaine Hydrochloride 0.25% without epinephrine
 
• 40cc Normal Saline
 
 Final Volume: 120cc	
 
• 60cc Bupivacaine Hydrochloride 0.25% without epinephrine
 
• 60cc Normal Saline
 
 Final Volume: 120cc	
 
• 120cc NORMAL SALINE
 

**Randomization**

Patients will be randomized using a computer-generated random allocation sequence, by the investigational pharmacy personnel. The random allocation sequence will be implemented with REDCap®, where a randomization allocation table will be generated and uploaded into REDCap® by the study statistician listed in this protocol. Randomization will occur during the operation at the end of adhesiolysis, and at the beginning of abdominal wall reconstruction, to allow for sufficient time for the investigational pharmacy to prepare and dispense the assigned intervention. This study will be double-blinded since patients will be blinded to their assigned intervention until their participation in the study is complete, and also surgeons will be blinded to the intervention assigned to the subject. Only the investigational pharmacy will be aware of the

assigned intervention and this information will be stored in the appropriate randomization platform in REDCap. The study coordinator and other research personnel who will be abstracting opioids doses and pain scores from patients will also be blinded to the intervention that was assigned to patients.

### **Surgical Procedure**

All patients will undergo the same operation, under a standard of care protocol. Our surgical approach to open ventral hernia repair with retromuscular mesh placement is further detailed. Skin preparation, hair removal, perioperative antibiotics and venous thromboembolism prophylaxis will be performed per Surgical Care Improvement Project protocol guidelines. The procedure will be performed through a midline incision. Upon entering the abdominal cavity, all adhesions between intra-abdominal contents and the anterior abdominal wall are routinely lysed using sharp dissection. When present, hernia contents are reduced back to the cavity. At the end of adhesiolysis, the surgeon will ask the OR nurse to contact the investigational pharmacy via telephone, who will randomize the subject. The investigational pharmacy will be responsible for preparing and dispensing the assigned intervention. The OR nurse will receive the drug from the investigational pharmacy in a standardized bag and will dispense it to the surgeon at the time of the TAP block. Neither the surgeon nor other members of the surgical team will be informed about which of the interventions were assigned to the specific patient. Electronic medical records will contain the information: "Patient was randomized and assigned to receive intervention according to randomization performed by investigational pharmacy."

Retromuscular hernia repair is performed initially incising the posterior rectus sheath just lateral to the linea alba. The release will be performed at least 5 cm above and below the fascial

defect, and retrorectus dissection is carried out laterally in the direction of the linea semilunaris.

If deemed necessary, a posterior component separation will be performed by incising the posterior lamella of the internal oblique, dividing the fibers of the transversus abdominis muscle and dissecting the preperitoneal and retroperitoneal spaces of the lateral abdominal wall laterally.

At the end of the myofascial release, the assigned intervention drug will be dispensed in syringes to the surgeon who will perform the perform a TAP block under direct visualization.

*The TAP block*

Injections of the designated drug (group 1, 2 or 3) will be performed under direct visualization by the attending surgeon, in 5 vertical levels, to the thoracoabdominal nerves (from T7 to T11).

Other details relating to administration will be per manufacturer's instructions (4).

The posterior sheath will be reapproximated, and a standard piece of polypropylene mesh will be placed in the retromuscular space.

Mesh type will be defined by the surgeon intraoperatively according to the patient and hernia-specific variables. Mesh fixation will be performed circumferentially using mechanical sutures. Closed suction drains will be placed above the mesh and in the subcutaneous space, and the timing of removal will be based on the surgeon's standard practice. Fascial closure and management of wound dressings will also follow the surgeon's standard practice.

## Multimodal Pain Management

For postoperative analgesia, all patients will also receive a patient-controlled analgesia (PCA) device according to the standard of care; **preferably:**

- Hydromorphone HCL 0.5mg/ml (Dilaudid®, Purdue Pharmaceuticals, Stamford, CT) in 100ml of normal saline, with no basal rate infusion, a patient bolus dose of 0.2-0.4mg, bolus interval of 6 minutes (maximum 10 doses per hour).

**In case there is a contraindication to Hydromorphone, alternative PCA regimens can be:**

- Morphine 1mg/ml in 100ml of normal saline, with no basal rate infusion, patient bolus of 1mg, bolus interval of 6 minutes (maximum 10 doses per hour) or,
- Fentanyl 20mcg/ml in 100ml of normal saline, with no basal rate infusion, a patient bolus of 20mcg, bolus interval of 6 minutes (maximum 10 doses per hour).

**No epidural analgesia will be administered.**

In addition, as part of the multimodal analgesia protocol for our enhanced recovery after surgery pathway, patients will also receive the following medications:

Acetaminophen	1G every 6 hours, after initiation of oral intake
Gabapentin	300mg every 8 hours, after initiation of oral intake
Oxycodone	5mg every 3 -4 hours as needed in the transition of weaning PCA, and after PCA has been discontinued

Although administration of Ketorolac Tromethamine (Toradol®, La Roche Inc.) is a part of the multimodal analgesia protocol of our ERAS pathway, its usage is according to patient age, comorbidities, renal function and ultimately at surgeon's discretion, and therefore, it will not be included in the postoperative pain management of the patients included in this study to avoid introducing bias to our results.

### **Rescue medication**

To ensure the comfort and adequate pain postoperative pain control, additional intravenous or oral opioids are allowed in the protocol, to be administered for breakthrough pain (as needed). Subjects should only receive rescue medication upon request, and for pain control.

Options for postsurgical rescue medication are:

- Hydromorphone 0.5mg/ml, 0.4mg administered intravenously; Dose can be repeated every 15 minutes, up to 3 doses. The sequence can be repeated every 6 hours if needed.
- Morphine 1mg/ml, 1 to 2mg administered intravenously; Dose can be repeated every 15 minutes, up to 3 doses. The sequence can be repeated every 6 hours if needed.
- Fentanyl 20mcg/ml, 25 to 50mcg administered intravenously; Dose can be repeated every 15 minutes up to 3 doses. The sequence can be repeated every 6 hours if needed.

**No other pain medications will be allowed in this protocol. All other aspects of postoperative management are standard of care and will occur at surgeon's discretion and guided by current best practices of the Cleveland Clinic Comprehensive Hernia Center.**

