## STUDY DESIGN

As in previous randomized controlled trials executed by our research group, the AHSQC will serve as a platform for data collection. Additional data not captured by the AHSQC will be recorded by a trained study coordinator or research fellow and uploaded into Research Electronic Data Capture ( RedCAP®). Baseline and intraoperative variables, as well as some of our outcomes of interest (30-day pain scores, hospital length of stay, PRQOL), are already captured within the AHSQC database, allowing for follow-up and data capture with minimal additional effort outside that of routine care (11).

This will be a double-blind, 3-arm, randomized controlled trial with a treatment 1: treatment 2: control allocation ratio of 1:1:1. No important changes to the methods after trial commencement are anticipated. We anticipate that this will be a single-institutional study of patients undergoing elective open ventral hernia repair at Cleveland Clinic Comprehensive

Hernia Center ( Main Campus, Cleveland Clinic Foundation, Cleveland, Ohio, USA) performed by 4 staff surgeons: [name] (PI), [name] (co-I), [name] (co-I) and [name] (co-I). Nonetheless, we do not discard to turn this trial into a multi-institutional trial in the future. No important changes to the methods after trial commencement are anticipated. No interim analyses will be performed, and no stopping guidelines are needed since the interventional arms of this study are already currently performed at our institution, and we do not anticipate adverse events requiring study suspension.

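### Four surgeons deliver the block and control the operation and non-analgesic aftercare, yet neither allocation nor analysis accounts for surgeon: a small, cheaply avoidable loss of precision, chiefly for length of stay

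*Combined protocol and SAP*

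**What the plan says.** **Who operates.** The Study Design section describes one centre, with operations "performed by 4 staff surgeons" and a "treatment 1: treatment 2: control allocation ratio of 1:1:1".

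**What the surgeon controls.** Under Surgical Procedure, the attending surgeon injects the block under direct vision at five levels, decides whether component separation is needed and chooses the mesh. For drains, "the timing of removal will be based on the surgeon's standard practice"; fascial closure and dressings are handled the same way. The Rescue medication section ends with a general clause, "All other aspects of postoperative management are standard of care and will occur at", and this clause then names who decides and within what bounds: "surgeon's discretion and guided by current best practices of the Cleveland Clinic Comprehensive Hernia Center".

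**What the surgeon does not control.** The sentence before that reads: "No other pain medications will be allowed in this protocol". PCA regimens, acetaminophen, gabapentin, oxycodone and rescue options are listed. Epidural analgesia is ruled out. Ketorolac is withdrawn, partly because its use depends on the surgeon's discretion.

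**Allocation.** "Patients will be randomized using a computer-generated random allocation sequence, by the investigational pharmacy personnel", using REDCap, "where a randomization allocation table will be generated and uploaded into REDCap® by the study statistician listed in this protocol". No stratification factor, block size or minimisation is mentioned.

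**Analysis.** The Statistical Analysis section compares pain, opioid use, length of stay and quality of life by Mann-Whitney test. It has no surgeon term and otherwise leaves the choice of test to the statistician.

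**The concern.** Surgeon is known before randomization and may affect the outcomes through how the block is delivered, how extensive the operation is, when drains come out and when the patient goes home. No discharge criterion is stated, so discharge falls under the general discretion clause, and length of stay is both a named aim and a secondary outcome. For 72-hour opioid use the remaining latitude is narrower: the PCA bolus range, the choice among listed rescue drugs, the time at which PCA stops (no criterion is stated) and the extent of the operation.

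The protocol accepts the principle when it removes ketorolac. The same thinking is not carried into the allocation or the analysis. If surgeons differ, the unadjusted test counts that difference as noise, in a trial sized for exactly 80% power.

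**Working it through.** **1. The plan's own figure.** The Power Calculation section gives a 30% reduction, alpha 0.05, 80% power and 49 per arm, but no mean or SD. The 49 can therefore only be solved backwards (two-sided test assumed): d = √(2 × (1.96 + 0.8416)² / 49) = 0.566, so the implied coefficient of variation is 0.30 / 0.566 = 0.53. With dropout, 49 × 1.1 = 53.9, or 54 per arm, and 3 × 54 = 162, as stated.

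**2. How uneven surgeons may be across arms.**
- With 54 per arm, near-equal caseloads (assumed) and no strata, the largest difference in any surgeon's share between two given arms is 10 percentage points or more in about 56% of simulated trials, and 15 or more in about 20%.
- With 49 per arm and caseloads drawn at random, the average largest difference is about 12 points, and it is 15 or more in 22–26% of trials. Blocking within surgeon cuts the average to about 1.5 points.

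**3. What that does to the treatment difference.** If surgeon explains a share s of outcome variance, the shift from chance imbalance has SD √(2s/54), in outcome SDs.
- s = 5%: √(0.10/54) = 0.043, which is 0.043/0.566 = 8% of the planned difference.
- s = 10%: √(0.20/54) = 0.061, which is 11%.

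**4. Bias or noise?** Across surgeon shares from 0 to 20%, simulated type I error of the unadjusted Mann-Whitney test without strata was 4.4–5.3%. The test already allows for this variation, so what is lost is precision.

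**5. Which change recovers it?** Two-arm simulation, 49 per arm, normal outcome, four equal caseloads, surgeon share 10%, 2,000 runs per setting (Monte Carlo error √(0.8 × 0.2/2000) = 0.9 point):

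| Allocation | Analysis | Power |
|---|---|---|
| No strata | Mann-Whitney | 77.6% |
| Within surgeon | Mann-Whitney | 78.7% |
| No strata | Surgeon-adjusted linear model | 82.3% |
| Within surgeon | Surgeon-adjusted linear model | 82.5% |

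The analysis carries most of the gain. Stratifying while keeping the unadjusted test makes it conservative: type I error 3.6% at a 10% share and 2.5% at 20%. The full 4.9 points should not be credited to surgeon, since the same two plans (first and last rows) differed by 81.2 − 78.8 = 2.4 points when surgeon explained nothing. That gap reflects simulation error and the linear model's advantage over ranks on normal data.

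**6. Rank-based options.** The plan treats its outcomes as non-normal, so a rank method is the natural choice.
- *Van Elteren test* (8,000 runs per setting). With stratified allocation, against the current plan: 79.2% versus 79.7% at a 5% share, 82.2% versus 80.4% at 10%, and 83.6% versus 80.7% at 15%. As an analysis-only change at shares of 0, 2 and 5%, power falls from 78.7, 79.8 and 79.7% to 76.0, 77.6 and 78.9%.
- *Regression of ranks on arm and surgeon*, with allocation blocked within surgeon: no detectable loss at 0–2%, a gain of about 2 points at 5% and of 3–4 points at 10–15%. As an analysis-only change it loses up to about 1 point if surgeon explains nothing.

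**The case against.** The strongest reply is that little is left for surgeons to vary. Analgesics are a closed list, the discretion clause is bounded by centre practice, the protocol says all patients have the same operation, and the block is specified. The opioid endpoint sums intravenous and oral doses as morphine equivalents, so the time at which PCA stops largely changes route. One centre and one recovery pathway also suggest a small between-surgeon variance. All of this stands. It is why the point is modest for opioid use and rests mainly on length of stay.

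Three stronger readings are tempting and are not supported:

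- *Surgeon imbalance biases the result.* Surgeons, patients and data abstractors are blinded, so discretion cannot systematically favour an arm, and simulated type I error stays near 5%. The imbalance percentages in step 2 describe caseloads, not outcomes.
- *Allocation is unstratified.* The Randomization section is silent. The supportable statement is that no stratification is stated.
- *Accounting for surgeon is worth extra patients.* One might compute 49/(1 − s) and obtain 52, 54 or 58 per arm for s = 5, 10 or 15%. That is an upper bound from an ideal linear model. The van Elteren test, an obvious choice for a stratified analysis, does not reach it, and s is not in the documents.

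**Conclusion.** The point holds as a minor one. Four surgeons control the extent of operation, drain timing and the non-analgesic care that the protocol leaves open, including discharge, while no stratification by surgeon is stated and the planned tests ignore surgeon. The consequence is lost precision, most plausible for length of stay and modest for 72-hour opioid use.

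The size depends on the share of outcome variance due to surgeon, which the documents do not give. With both changes the gain is about 0 power points for a share of 0–2%, 2 for 5% and 3–4 for 10–15%. These figures assume a normal outcome, 49 evaluable patients per arm, equal caseloads and surgeon variance already inside the planned SD. If surgeon variance instead came on top of that SD, unadjusted power would be 78.0% at a 5% share and 75.7% at 10%, against the planned 80%.

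**What to change.** - **Randomization section:** state the allocation method, with the REDCap table generated in permuted blocks within surgeon (four strata). The surgeon's identity can be given in the telephone call that already goes to the investigational pharmacy.
- **Statistical Analysis section:** compare length of stay, opioid use and pain with a pre-specified surgeon-adjusted rank-based model, for example regression of ranks on arm and surgeon. Prefer this to the van Elteren test, which loses power when surgeon variance is small.
- **If patients are already randomized without strata:** make only the analysis change. It carries most of the benefit.

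The two changes belong together, because stratified allocation followed by an unadjusted test is conservative.

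**Cost:** one new table and a sentence in each section, with no extra patients or procedures. The downsides are a few incomplete blocks at the end of enrolment, three degrees of freedom, and up to about 1 power point if surgeon explains nothing and only the analysis is changed.

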### **Exclusions from the study during participation**

Patients will be excluded from participation in the trial if:

- Remain intubated for more than 12 hours after the end of operation due to any reason since important part of the assessments will not be performed
- Experience any medical event that demands management with opioid medications that are used not exclusively for pain management (for example, patients placed in mechanical ventilation who receive continuous infusion of opioids)

Also, patients can be excluded from the study at any moment during the trial if they withdraw consent or according to clinical judgment of the PI.

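### Patients can be excluded after randomization for postoperative events or on PI judgment, and no stated analysis set keeps them in the primary comparison

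*Combined protocol and SAP*

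**What the plan says.** *Randomization* fixes the time of allocation: "Randomization will occur during the operation at the end of adhesiolysis". *Surgical Procedure* places the block later in the same operation, after the myofascial release.

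*Exclusions from the study during participation* then opens with "Patients will be excluded from participation in the trial if" and gives two event-based grounds:

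- first, "Remain intubated for more than 12 hours after the end of operation due to any reason", which the protocol justifies with "since important part of the assessments will not be performed" and nothing further;
- second, "Experience any medical event that demands management with opioid medications that are used not exclusively for pain management".

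It adds that "patients can be excluded from the study at any moment during the trial if they withdraw consent or according to clinical judgment of the PI". No criteria for that judgment are given.

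*Statistical Analysis* lists summaries and tests: medians with interquartile ranges, and Mann-Whitney U tests for opioid use, pain, length of stay and quality of life. It does not say which patients are analysed, gives no missing-data rule and plans no sensitivity analysis. *Power Calculation* allows 10% for losses to follow-up and does not mention these exclusions.

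On blinding, *Randomization* says that "surgeons will be blinded to the intervention assigned to the subject" and that "other research personnel who will be abstracting opioids doses and pain scores from patients will also be blinded".

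**The concern.** Both event-based grounds arise after allocation and normally after the block has been given, so they can depend on treatment. Randomization protects a comparison only if patients stay in the arm to which they were assigned. If patients with a difficult postoperative course are removed, and more of them from one arm than another, the remaining groups differ for a reason other than the drug's effect on opioid need.

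The second ground is defined by opioid exposure, which is closely tied to the primary outcome. The third is open-ended. With no analysis set named, whether to keep these patients could be decided once data are in hand. The drop-out allowance replaces lost numbers; it does not restore comparability.

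**Working it through.** **1. Does the stated reason require removal?** Set against how each outcome is collected:

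| Outcome | Source in the protocol | Lost if the patient stays intubated? |
|---|---|---|
| In-hospital VAS pain | Asked of the patient | Yes, while intubated |
| Opioid dose | Abstracted by research staff (*Randomization*) | No |
| Length of stay | Routine AHSQC data (*Secondary Outcomes of Interest*) | No |
| 30-day PROMIS and HerQLes | AHSQC patient-reported outcomes | Not for this reason |

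The reason fits VAS scores only.

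**2. Could removal depend on arm?** Two routes are possible, in opposite directions. *Patient Risks and Discomforts* lists seizures, arrhythmias and dyspnea for bupivacaine, and rare seizures and cardiac arrest for Exparel. Placebo is saline, so toxicity could remove more active-arm patients. Both active arms contain the same 60 cc of bupivacaine, so that shared risk should largely balance between them. Against this, the *Introduction* refers to opioid side effects and hypothesizes lower opioid use on Exparel, so opioid-related events could be more frequent on placebo.

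**3. The plan's own figures.** 49 × 1.10 = 53.9, rounded up to 54 per arm; 3 × 54 = 162. Both reproduce. (49 / 0.90 = 54.4 would give 55; the difference is immaterial here.) No mean or SD is given. A two-sample t-test with 49 per arm, two-sided 0.05 and 80% power needs a standardized difference of 0.572. A 30% reduction then implies SD/mean of about 0.525.

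**4. Illustration.** The documents give no removal rates, so everything in this step except the 30%, the 54 and the implied SD/mean is assumed.

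- Opioid use is lognormal with SD/mean 0.525, and the true reduction is 30%.
- In each arm 10% of patients are atypical, with mean use k times the arm mean; the other 90% have mean (1 − 0.10k)/0.90 times the arm mean.
- A fraction p of the arm is removed, all from the atypical group. The atypical share left is w = (0.10 − p)/(1 − p): 0.082 at p = 2%, 0.063 at 4%, 0 at 10%.
- The median m(p, k) of those left solves (1 − w)·F(typical) + w·F(atypical) = 0.5.
- Apparent reduction = 1 − 0.70 × m(Exparel)/m(placebo).
- k = 2 or 3 if opioids given for sedation count in the total; k = 0.3 if they do not.

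| Removed, Exparel / placebo | k = 2 | k = 3 | k = 0.3 |
|---|---|---|---|
| 4% / 2% | 30.8% | 30.9% | 29.0% |
| 6% / 2% | 31.7% | 31.9% | 28.1% |
| 10% / 2% | 33.3% | 33.7% | 26.1% |
| 2% / 4% | 29.2% | 29.0% | 30.9% |
| 2% / 6% | 28.3% | 28.1% | 31.9% |
| 2% / 10% | 26.5% | 26.1% | 33.7% |
| 6% / 6% | 30.0% | 30.0% | 30.0% |

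The shift is about 1, 2 and 4 points, and zero when removal is equal. The sign depends on which arm loses more and on whether sedation opioids count.

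**5. Type I error.** Mann-Whitney test, no true effect, 54 per arm before removal, 20,000 simulated trials per case (simulation standard error about 0.002), either arm losing more:

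| Removal | Type I error |
|---|---|
| Everyone kept, or 6% in each arm | 0.046–0.053 |
| 4% vs 2% | 0.050–0.055 |
| 6% vs 2% | 0.058–0.065 |
| 10% vs 2% | 0.085–0.106 |

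In patients, 2%, 4%, 6% and 10% of 54 are about 1, 2, 3 and 5. The 10% case removes every atypical patient in one arm and uses that arm's whole drop-out allowance (54 − 49 = 5). Fixing the number of atypical patients per arm lowers that case to 0.071–0.079.

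**The case against.** **The rule concerns participation, not analysis.** This stands. A reader might infer that the protocol orders these patients out of the analysis. It does not say so. That is only the likely reading, because nothing keeps them in. What is certain is that the analysis population is unstated.

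**The mechanism is thin.** This stands in part. A reader might infer that toxicity would remove more active-arm patients and so bias the result in a known direction. No listed drug risk is linked to either trigger. The first ground concerns patients who stay intubated, so a toxic event after extubation would not meet it. The placebo route in step 2 points the other way.

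**Blinding protects the trial.** It does so against deliberate selection: surgeons, among them the PI (*Study Design* lists the PI as one of the four), and data abstractors are blinded. It cannot prevent removal caused by events that the treatment itself influences.

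**The effect is small.** At modest imbalance it is. At 4% against 2% the type I error cannot be told apart from that with everyone kept. Calculations on means give larger shifts, but the plan reports medians and tests ranks.

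**Keeping everyone has its own problem.** This stands and shapes the fix. *Primary outcomes of Interest* lists PCA, intravenous rescue and oral opioids, then refers to the total dose used, most naturally the total of those sources. On that reading sedation opioids do not count. A ventilated patient who can neither operate a PCA nor request rescue would then rank as a low opioid user, so a serious complication would look like success. A rank test does not correct that.

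**Conclusion.** The point holds as a weakness in a stated rule that should be fixed. The protocol excludes patients after randomization, one ground has no criteria, and no analysis set retains them. Confidence is high on those facts. Bias is possible but not demonstrated: it is zero if removal is unrelated to arm, and otherwise unknown in direction.

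Its size rests wholly on assumed removal rates and on the assumed opioid use of those removed. On those assumptions it is about 1 point on a 30% reduction in medians at 4% against 2%, and about 4 points with type I error near 0.08 to 0.11 only in the extreme case. A reader might infer that the primary result will be materially biased; the documents do not support that. The case for acting is that the threat is avoidable at very little cost.

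**What to change.** - State that the primary analysis includes all randomized patients in their assigned arm.
- Let the exclusion rules end study-specific assessments only. Keep opioid dose, length of stay and 30-day AHSQC data unless consent is withdrawn.
- State that PI judgment is not a ground for leaving the analysis.
- Together with this set, prespecify how the 72-hour opioid outcome is scored for these patients: whether opioids given for sedation count, recorded separately in either case, and, if they do not count, a rule such as worst rank so that a ventilated patient is not scored as a good outcome.
- Use all available VAS scores.
- Report exclusions by arm with reasons, and give the analysis that applies the exclusions as a sensitivity analysis.

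The cost is protocol and analysis wording plus chart abstraction for a few patients. The downside is that a few atypical or rule-assigned opioid values enter the primary analysis and some VAS scores stay missing. Sample size and patient care do not change.
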